8.14 Investigational Site Termination

ArthroX reserves the right to terminate an investigational site for any of the following reasons:

- Failure to secure subject informed consent or Authorization for the Use and Disclosure of Health Information prior to study enrollment
- Failure to report unanticipated adverse device effects within 24 hours of discovery to sponsor or monitor and ten days (to the IRB) of learning of the effect
- Failure to report serious adverse device effects within 24 hours of discovery to ArthroX.
- Repeated investigational plan violations
- Repeated failure to appropriately complete case report forms
- Failure to enroll an adequate number of subjects
- Loss of or unaccounted for investigational product inventory
- Administrative decision by the company

8.15 Final Monitoring Visit

Upon completion of the clinical study (when all subjects enrolled have completed the follow-up visits, the data collection and queries have been completed, and no additional information is required of the site for data management / statistical review), a final study close-out visit will be conducted by the Study Monitor. The study monitor will verify disposition of investigational devices and review regulatory documents to confirm that the investigator's regulatory files are current and complete, and that any outstanding issues from previous visits have been resolved. Other issues that will be reviewed at this visit include, but are not limited to: long-term retention of study files, possibility of site audits, publication policy, and verification that the investigator will notify the IRB regarding study closure. A final follow-up letter will be drafted and submitted to the Investigator to document that all investigational plan-related activities have been completed and that the clinical study is completed and may be closed at the site.

The monitor may conduct close out activities remotely if the Eclipse Shoulder Prosthesis receive 510 (k) clearance and this study is terminated prematurely.

8.16 Protocol Amendments

All protocol amendments must be approved by ArthroX Inc. All amendments must have FDA approval in addition to IRB approval.

8.17 Protocol Deviations and Violations

Protocol deviations are defined as any event where the clinical investigator or site personnel did not conduct the study according to the protocol.

Any protocol deviations undertaken to protect the life or physical well-being of a subject in an emergency situation must be reported to the

ArthroX Clinical Research within 48 hours of occurrence and the respective IRB as soon as possible, but in no event later than five calendar days after the emergency occurs.

Departures to protocol are often situations where unforeseen circumstances are beyond the investigator's control (e.g., subject did not attend scheduled follow-up visit, blood sample lost by laboratory, etc.); however, the event is still considered a protocol deviation and requires documentation as such.

Subject-specific deviations will be reported in the EDC.

Study deviations are classified as follows:

- Informed Consent Form (ICF)
 - Wrong ICF version signed
 - Other deviation related to informed consent version.
- Protocol
 - Study procedure not done per protocol
 - Study procedure or visit not done
 - Study procedure or visit Out of study window
 - Other procedure not done per protocol
- Eligibility
 - Subject did not meet eligibility criteria
 - Other deviation related to eligibility criteria
- Source Document
 - Missing or incomplete source document
 - Other deviation related to source document
- Regulatory
 - Subject enrolled without IRB approval

- Other deviations related to Regulatory

Non-subject specific deviations or violations, (e.g. unauthorized use of an investigational device outside the study, unauthorized use of an investigational device by a physician who has not signed an investigator agreement, etc.), will also need to be reported to ArthroX Clinical Research via EDC. Investigators will also adhere to procedures for reporting study deviations and violations to their IRB in accordance with their specific IRB reporting policies and procedures.

Regulations require that investigators maintain accurate, complete and current records, including documents showing the dates of and reasons for each deviation from the protocol.

8.18 Publication

The publication of the principal results from any single center experience within the trial is not permitted, and any exceptions to this rule require the prior approval from ArthroX, Inc.

8.19 Audits / Inspections

In the event that audits are initiated by the sponsor, its designee, or FDA, the investigator will allow access to the original medical records and provide all requested information.

9 Adverse Events Definitions

9.1 Definitions

9.1.1 Adverse Events

An adverse event (AE) is any undesirable experience (e.g., sign, symptom, illness, clinically significant abnormal laboratory value, or other medical event) occurring in a subject during the course of the study, whether or not it is related to the investigational device or procedure.

An AE does include a/an:

- Exacerbation of a pre-existing illness
- Increase in frequency or intensity of a pre-existing episodic event or condition
- Condition detected or diagnosed after study device use even though it may have been present prior to the start of the study
- Continuous persistent disease or symptoms present at baseline that worsen following the start of the study

An AE does not include a/an:

- Medical or surgical procedure (e.g., surgery, endoscopy, transfusion); the condition that leads to the procedure is considered an AE
- Pre-existing diseases or conditions present or detected at the start of the study that do not worsen
- Situations where an untoward medical occurrence has not occurred (e.g., hospitalizations for cosmetic elective surgery, social and/or convenience admissions)
- The disease or disorder being studied, or sign or symptom associated with the disease or disorder, unless the disease, sign or symptom is more severe than expected based on the subject's condition and/or requires intervention.

9.1.2 Serious Adverse Events

A Serious adverse event is an adverse event that:

- led to death,
- led to serious deterioration in the health of a subject that
 - resulted in a life-threatening illness or injury,
 - resulted in permanent impairment of a body structure or body function,

- required inpatient hospitalization or prolongation of existing hospitalization,
- resulted in medical or surgical intervention to prevent permanent impairment to a body structure or a body function.
- led to fetal distress, fetal death or a congenital anomaly or birth defect.
- The following clarifications are provided for the serious adverse events:
 - Life-threatening means that the subject was, in the view of the investigator, at immediate risk of death from the event as it occurred. The definition does not include an event that, had it occurred in a more severe form, might have caused death.
 - Hospitalization for elective treatment of a pre-existing condition that did not worsen during the study is not considered a serious adverse event.
 - “Inpatient” hospitalization means the subject has been formally admitted to a hospital for medical reasons. This may or may not be overnight. It does not include presentation at a casualty or emergency room.
 - Important medical events that may not result in death, or be life-threatening, however based upon appropriate medical judgment, may jeopardize the subject and may require medical or surgical intervention to prevent one of the outcomes listed in this definition.
 - Is significant for any other reason.

9.1.3 Anticipated Adverse Events:

Anticipated adverse events are those events that are reasonably expected to occur as a result of the subject’s disease state or treatment. For this study, anticipated adverse events associated with the procedure or post-procedure include, but are not limited to, the following;

- Infections, both deep and superficial
- Allergies or other reaction to device materials
- Temporary or permanent nerve damage as a result of surgery, pressure or hematoma.
- Bruising (hematoma)
- Cardiovascular complications including venous thrombosis, pulmonary embolism, and cardiac arrest.
- Delayed wound healing.

Device-related adverse events are those events that can be directly attributed to the study device and are adjudicated as such by the investigator. These events may include, but are not limited to:

- Infections, both deep and superficial
- Allergies or other reaction to device materials
- Loosening of the implant as a result of changed condition in load transfer, respectively fatigue wear or tissue reaction to implant or as result of inadequate anchoring technique.
- Dislocation, subluxation or inadequate scope of movement as a result of failure to achieve optimum positioning of the implant.
- Joint stiffness, pain, and swelling
- Bone fractures as a result of one-sided overload or weakened bone structure.
- Temporary or permanent nerve damage as a result of pressure or hematoma.
- Bruising (hematoma) and delayed wound healing.

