3.2.2 Primary Endpoint

The primary safety and effectiveness endpoint is 2 Year Composite Clinical Success requiring the following:

- An improvement in the Adjusted Constant Score (for pain, function and range of motion) from baseline (pre-op) to the Month 24 time-point that is ≥ 10 points and a final Adjusted Constant Score ≥ 54 .

- Radiographic success at the Month 24 time-point which is defined as absence of clinically significant humeral radiolucency, humeral migration/subsidence (relative to 3 month time point), glenoid radiolucency, glenoid migration/subsidence (relative to 3 month time point), device disassembly or fracture, and/or periprosthetic fracture, as described in the radiographic protocol
- No reoperation, removal, or modification of any study component up to the subject's completion of the study.
- No serious device-related complications up to the subject's completion of the study.

For a patient to be considered a success, he or she must meet all of the above criteria.

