8.12 Investigational Site Training

Study conduct-specific training of clinical trial personnel is the responsibility of Arthrex's CRA, the study monitor and the Investigator. Study training will occur before the first device use. The investigator is responsible for ensuring that his/her staff conducts the study according to protocol. To ensure compliance with the Investigational Plan and regulatory requirements as well as accurate data collection, site training will include a detailed review of this Investigational Plan, Electronic Data Collection (EDC), adverse event reporting, device handling and inventory, monitoring logistics, and regulatory requirements.

Arthrex's CRA or the study monitor will ensure that study personnel:

- Submit this Investigational Plan to their IRB for appropriate review and obtain written approval for the conduct of the study prior to consenting any subject for this study;
- Maintain all study correspondence, this Investigational Plan, and all related and required records on file at their facility, and
- Confirm the investigator understands his/her full responsibility for the study investigation at their individual medical practices, clinics, or medical facilities.

Procedure and Training

All Investigators and site personnel participating in the study will receive device-specific detailed training from Arthrex personnel.

Physician Hands-on Training

All Investigators will have experience with arthroplasty surgery, in addition to being instructed on the specifics of the Eclipse™ and the Univers™ II Shoulder Prosthesis. After instruction from a qualified Arthrex trainer, the physician will demonstrate successful application of the study device either in Sawbones or

cadaver specimen. In addition, an ArthroX “corporate team member” or designee will be present for the each Investigator’s first surgical case.

All training will be documented prior to first use of the study device.

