9.2 Adverse Event Documentation

Adverse event information will be collected on all subjects. All adverse events must be reported in the source documents and in the EDC. Adverse events will be evaluated by the investigator and differentiated by:

- Seriousness, as defined in Section 9.1.2
- Severity of the event, defined below.
 - **Mild:** Awareness of signs and symptoms, but easily tolerated; are of minor irritant type, causing no loss of time from normal activities; symptoms would not require medication or a medical evaluation; signs and symptoms are transient.

- **Moderate:** Discomfort severe enough to cause interference with usual activities; requiring treatment, but not extended hospitalization or intensive care for the subject.
- **Severe:** Incapacitating with inability to do work or usual activities; signs and symptoms may be systemic in nature or require medical evaluation and/or treatment; requiring additional hospitalization or intensive care (prolonged hospitalization).
- Relatedness to the device or procedure, defined as:
 - **Unrelated:** AE is due to the underlying disease state or concomitant medication or therapy not related to the study-specific devices or procedures.
 - **Probably not Related:** AE had minimum or no temporal relationship to the study-specific devices or procedures and/or more likely alternative etiology exists.
 - **Possibly Related:** AE had a strong temporal relationship to the study-specific devices or procedures and alternative etiology is equally or less likely compared to the potential relationship to the study-specific devices or procedures.
 - **Probably Related:** AE had a strong temporal relationship to the study-specific devices or procedures and another etiology is unlikely.
 - **Unknown:** Relationship of the AE to the study-specific devices or procedures and alternative etiology is unknown.

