9.3 Adverse Event and Unanticipated Adverse Device Effect Reporting

At every subject encounter, the investigator will determine if there has been an adverse event since the last encounter.

For this study, serious adverse events must be reported immediately (within 24 hours) directly to ArthroX, Inc. by completing the Adverse Event form and entering it into EDC. At the time of the initial report, the outcome (resolution status) may not be known. Updated information must be entered into EDC until final resolution of the event.

Unanticipated Serious Adverse Device Effects must also be reported by the investigator to the approving IRB as soon as possible, but not later than 10 working days after the investigator first learns of the effect. The sponsor must report to the FDA, all reviewing IRBs and participating investigators within 10 working days of notification from the investigator of a USADE.

The medical monitor will provide medical surveillance on adverse events and will evaluate all Serious Adverse Events (SAEs).

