9.5 Safety Monitoring

As the study sponsor of this clinical study, Arthrex Inc. will be responsible to monitor it for safety. In the circumstance where unanticipated adverse device event or serious adverse events occur due to a procedure, Arthrex, Inc., will convene a review committee which will determine any unreasonable risk to subjects, or if the study should be reviewed for modification or early termination.

10 Statistical Method and Sample Size Calculation

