5. Lack of serious device related complications (defined as a severe device-related adverse event) up to the subject's completion of the study.

Per the World Health Organization Definition of adverse events, a Grade 3 (or severe) adverse event significantly limits the patient's ability to perform routine activities despite symptomatic therapy.

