10.7 Safety Analysis

All safety endpoints will be summarized separately for investigational and control groups. Similarly, listings with details of the specific complications will be summarized separately as well.

The CCS Component Safety endpoint is any serious, definitely device-related adverse event within 24 Months of surgery. This will be evaluated at the exact two year anniversary (i.e., relative day 730) after the implantation surgery. The safety hypothesis of investigational verses control equality in the likelihood of serious device-related adverse event will be tested using a two-sided Fisher's Exact Test with Type I error rate set to $\alpha=0.05$.

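### Device-relatedness, a pass/fail part of the primary composite, rests on the investigator's unmasked judgement, and the medical monitor who already evaluates every SAE has no role in the endpoint

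*Combined protocol and SAP*

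**What the plan says.** **Who decides.** Section 9.1.3: "Device-related adverse events are those events that can be directly attributed to the study device and are adjudicated as such by the investigator". Section 9.2 gives the same person the grading of seriousness, severity and relatedness: "Adverse events will be evaluated by the investigator and differentiated by".

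**What the decision feeds.** Item 5 of the CCS list in Section 10.1 reads "Lack of serious device related complications (defined as a severe device-related adverse event". Section 10.7 puts the same component differently: "The CCS Component Safety endpoint is any serious, definitely device-related adverse event within 24 Months of surgery". Section 3.2.2 makes the composite all-or-nothing: "For a patient to be considered a success, he or she must meet all of the above criteria".

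**Who else looks at events.** Section 9.3: "The medical monitor will provide medical surveillance on adverse events and will evaluate all Serious Adverse Events (SAEs". Section 9.5 says that, after certain events, the sponsor "will convene a review committee which will determine any unreasonable risk to subjects, or if the study should be reviewed for modification or early termination". Neither provision mentions the CCS, and the text describes no clinical events committee or masked event review.

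**How another component is handled.** Radiographic findings go to two independent radiologists, each blinded to the other's reading, with a third resolving disagreements (radiographic protocol, Section 3.2).

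**The concern.** Investigator attribution is normal for adverse event reporting. Here it also decides whether a patient is a success or a failure in the primary test. No masking of investigators is described. Section 8.12 says "All Investigators will have experience with arthroplasty surgery" and has them instructed on both devices, one of which has no stem (Section 2.3) while the other does (Section 2.4). An assessor who operates or reads the follow-up films will know the arm.

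Whether a serious event is due to the device, the operation, the bone or the underlying disease is a judgement. Infection, haematoma, delayed healing and nerve damage appear in Section 9.1.3 under both the procedure and the device headings. If the judgement leans one way for the new implant and another for the familiar one, the CCS difference moves without any true difference. Leniency towards Eclipse would raise the type I error. Readiness to blame the novel implant would cost power.

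**Working it through.** **1. The plan's own figure.** Inputs from Section 10.4: CCS 0.88 in both arms, margin 0.10, one-sided alpha 0.05, power 80%, 2:1 allocation.

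n(control) = (1.645 + 0.842)² × (0.88×0.12 + 0.88×0.12/2) / 0.10² = 97.9, so 98 control and 196 Eclipse, 294 in all. This matches the plan. 294/0.85 = 346, against the stated 347. The point does not change the planned size.

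**2. Who can change the CCS call.**

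| Section | Role | Stated effect on CCS relatedness |
|---|---|---|
| 9.1.3, 9.2 | Investigator | Decides |
| 9.3 | Medical monitor | None stated |
| 9.5 | Sponsor's review committee | None; covers unreasonable risk and study modification |

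**3. Whether the threshold is defined.** CCS item 5 uses *severe* and device-related. Section 10.7 uses *serious* and *definitely* device-related. The scale in 9.2 runs unrelated, probably not, possibly, probably, unknown, with no definite grade. A rating recorded under 9.2 therefore cannot be mapped to the component as 10.7 states it. The monitor's remit in 9.3 is *serious* events, so a severe but non-serious event that counts under item 5 falls outside it.

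**4. Size of a differential.** Assumptions, none from the documents: a share p = 5% to 8% of patients has a serious event that could be device-related; attribution is 60% in Eclipse and 90% in control; a share v = 50% to 80% of these patients fails CCS on another component anyway.

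Net shift = p × (0.90 − 0.60) × (1 − v)

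- No overlap (upper bound): 0.05 × 0.30 = 1.5 points; 0.08 × 0.30 = 2.4 points.
- Low end: 0.05 × 0.30 × 0.20 = 0.3 points.
- High end: 0.08 × 0.30 × 0.50 = 1.2 points.

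Against the 10-point margin this is 3% to 12%, with 15% to 24% as the no-overlap bound. At 88% success, expected failures are 12%, so 5% to 8% would be 42% to 67% of all failures (5/12, 8/12). The event share is on the generous side.

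**5. What the shift b does to the test.** Let SE = √[pC(1−pC)/nC + pE(1−pE)/196] and P(declare non-inferior) = Φ[(pE − pC + 0.10)/SE − 1.645]. For type I error, pC = 0.88 and pE = 0.78 + b. For power under a shift against Eclipse, pE = 0.88 − b. Section 3.1 allows control randomization to stop after 77, so that case is shown too.

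| Shift b | Type I error, 98 controls | Type I error, 77 controls | Power if b is against Eclipse, 98 controls |
|---|---|---|---|
| 0 | 5.0% | 5.0% | 80.0% |
| 0.3 points | 5.7% | 5.7% | 77.6% |
| 1.2 points | 8.5% | 8.2% | 69.6% |
| 1.5 points (bound) | 9.7% | 9.3% | 66.8% |
| 2.4 points (bound) | 13.8% | 12.9% | 57.7% |

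Of 196 Eclipse patients, 1.2 points is 0.012 × 196, or about 2.4 patients.

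**The case against.** The best case against the point has four parts.

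- **The definition limits discretion.** The list in 9.1.3 names loosening from poor anchoring, dislocation from poor positioning and fracture in weakened bone as device-related. Blaming technique or bone does not by itself remove an event from the category. This stands in part: the list is illustrative, so discretion remains.
- **Many such events fail CCS anyway.** Reoperation, core-lab radiographs and the Adjusted Constant Score need no attribution by the investigator. This stands, and it is why the overlap term is in the calculation.
- **Other safeguards exist.** Section 8.10 has safety data fully verified against source, and Section 10.7.2 lists all serious and all severe events. These allow a check afterwards but do not change the primary result. The case report forms and the Monitoring Plan are not in the text, so a monitor's rating field cannot be ruled out.
- **A rule that counts either rating only adds failures.** It cannot correct over-attribution to the new implant. This stands, and the fix includes an attribution-free analysis for that reason.

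A reader might infer that investigators will favour Eclipse, or that the estimate is biased by the full 1.5 to 2.4 points. The documents support neither. Both implants are the sponsor's, investigators are instructed on both, no attribution rates are given, and the direction could be the reverse. That the assessor is the implanting surgeon is also an inference; nothing requires it or prevents it.

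**Conclusion.** The point holds as a modest weakness of design. The investigator is the only named adjudicator of a component that can fail a patient on the primary endpoint, and the inference that this person knows the arm is firm. The monitor's existing review is not used for the endpoint. Under the stated assumptions the distortion is about 0.3 to 1.2 points, taking a nominal 5% one-sided error to about 5.7% to 8.5% with 98 controls, or lowering power to about 78% to 70% if the lean is against Eclipse. The direction is unknown, and the event share, attribution rates and overlap are all assumed. The mismatch between *severe*, *serious* and *definitely* related needs no assumption: it is in the text and must be settled before any rating can be applied to the endpoint.

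**What to change.** 1. Reconcile CCS item 5 in Section 10.1, Section 10.7 and the scale in 9.2 into one stated threshold of seriousness or severity and of relatedness, using grades that the scale contains.
2. In 9.3 and 10.7, have the existing medical monitor record a relatedness rating for every event that could meet that threshold, including severe non-serious events. The rating is made before seeing the investigator's, from a narrative with the implant name removed where possible.
3. Prespecify three CCS analyses: under the investigator's rating; with an event counted if either rater calls it device-related; and with every serious or severe target-shoulder event counted whatever its attribution. Report the non-inferiority conclusion under each. The third does not depend on attribution, so it addresses bias in both directions.

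**Cost.** One data field, a slightly wider monitor remit, and slightly more CCS failures in the stricter versions. As an illustration, if success fell by an assumed two points in both arms, to 0.86, SE = √(0.86 × 0.14 × 3/196) = 0.0429 and power = Φ(0.10/0.0429 − 1.645), about 75% rather than 80%. The monitor's independence from the sponsor is not stated and should be.
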